7.3 Study procedures

Study procedure of the total study period

Thirty-five healthy subjects (male and female, any ethnic background, 18-65 years old) with overweight (BMI 25-30 kg/m²) will be recruited (for more information on recruitment and consent see section 10.2; inclusion criteria in section 4.2, exclusion criteria in 4.3). If the volunteer is interested, an appointment will be made to sign the consent and complete the medical screening (discuss questionnaire (medical history, health status and medicine, and physical activity level (low, moderate or active)). If the volunteer is suitable, we will measure height and body weight as described below). After the subject is included, (s)he will receive an introduction lecture (of about half an one hour) and two test days (that consist of about four hours) will be scheduled per participant (with at least seven days in between the test days). Both test days will be scheduled in a period of a month.

Height measurement for BMI calculation- Height will be measured using a standard stadiometer. The participant has to remove any footwear. All participants should have their height measured while in bare or stocking feet. The participant will be instructed to stand on the base of the stadiometer, and the investigator will check if the participant is standing straight with shoulders back and resting flat on his/her feet. The height will be recorded in centimetres (cm) to the nearest 0.1 cm.

Body weight measurement- Body weight will be measured using an electronic or digital scale, which is regularly calibrated. Subjects are asked to remove their footwear, outer garments (e.g., jackets, hats, heavy sweaters, etc.), belt, heavy jewellery, and they are asked to empty their pockets. The participant will be asked to remain on the scale, and the investigator will read the screen once stabilized and record the value in kg to the nearest 0.1 kg.

Procedure of the intervention study days

The procedure of the intervention study days is summarized in Table 3. On each test day, the subjects will arrive at 8:50 am at Maastricht University, after a ten hour fast, so no eating and drinking is allowed other than *ad libitum* consumption of water and tea (without milk or sugar) after 22:00 the night before each test day.

Upon arrival at Maastricht University (8:50 am), compliance to the previously mentioned rules will be checked and baseline measurements will be done ("t=0" min), including nine VAS scores for satiety and GI symptoms. Then, the experiment starts with the ingestion of a standardized breakfast (9:00 am, t=0 min). During all study days, this breakfast will be relatively light (± 120 kcal) and low in fat (≤ 0.5 g total lipid): 1 sandwich (tijgerbrood tarwe 1 g lipid/100g, 1 boterham: 35g (± 84 kcal)) with marmalade (0 g lipid/100g, 1 portion: 15g (± 36 kcal)) and one glass of water or tea (150 mL).

Ninety minutes after breakfast (10:30 am, t=90 min), once major part of the breakfast has been emptied from the stomach, subjects receive a low-fat yoghurt-like product of 0.20 L that contains one of the two formulations of emulsified safflower oil (6 g lipid as active or control formulation, for product details see section 5), following a randomized cross-over design. Each 30 minutes before the intervention and each 15 minutes after the intervention, the nine VAS scores for satiety and GI symptoms will be measured. Two hours after the intervention yoghurt (12:30, t=210 min), *ad libitum* meal intake will be measured as amount eaten from a large pasta meal (>1 kg, obtained from a local supermarket). After collection of these results, the test day is finished and the subject returns home (around 13:00 am). For an overview of the complete study design, see Figure 1.

VAS scores for satiety and GI symptoms- During a test day, satiety and GI symptoms will be measured at 12 time points (t= 0, 30, 60, 90, 105, 120, 135, 150, 165, 180, 195, 210 min). Questionnaires will be used to measure satiety feelings (satiety, fullness, hunger, desire to eat, desire to snack) and GI symptoms (bloating, discomfort, pain, nausea). These nine attributes will be measured using Visual Analogue Scales (VAS, 0 to 100 mm) scores, with the most negative or lowest intensity feelings at the low end and the opposing terms at the high end. The subject will be asked to indicate his feeling at that moment. The investigator can easily quantify the rating as shown in previous studies (for example: METC 13-2-025; 11-3-034; 14-3-062). The scoring forms will be collected immediately so that they cannot be used as a reference for later scorings.

Table 3. Schedule of the participant prior and during the test days.

When?	Action/Intervention	Measurement
Interview	Sign consent , complete screening (inclusion); and information lecture	Screening questionnaire, height, body weight
Test days (2x)		
8:50 am	Arrival* and baseline	VAS (S & GI, t=0 min)**
9:00 am	Standardized breakfast(t=0 min)	
9:30 am		VAS (S & GI, t=30 min)
10:00 am		VAS (S & GI, t=60 min)
10:30 am	Intervention yoghurt(t=90 min)	VAS (S & GI, t=90 min)**
10:45 am		VAS (S & GI, t=105 min)
11:00 am		VAS (S & GI, t=120 min)
11:15 am		VAS (S & GI, t=135 min)
11:30 am		VAS (S & GI, t=150 min)
11:45 am		VAS (S & GI, t=165 min)
12:00 am		VAS (S & GI, t=180 min)
12:15 am		VAS (S & GI, t=195 min)
12:30 am	Ad libitum lunch(t=210 min)	VAS (S & GI, t=210 min)**
13:00 am	Return home	

VAS= Visual Analogue Scales for satiety (S) and GI symptoms (GI). * after 10 h fasting. ** VAS score measured just before the intervention.

7.4 Withdrawal of individual subjects

Subjects can leave the study at any time for any reason (also without reason) if they wish to do so without any consequences. The responsible investigator can also withdraw a subject if continuing participation is in his opinion deleterious for the subject's wellbeing. Subjects can also be withdrawn in case of protocol violations and non-compliance. When a subject withdraws from the study, a medical examination can be performed if considered necessary by the nurse practitioner/physician. In case of withdrawal because of AEs or SAEs haematological, blood chemistry and urine laboratory test or other special examinations may be performed.

7.4.1 Specific criteria for withdrawal

Not applicable.

7.5 Replacement of individual subjects after withdrawal

Thirty-five subjects will be included at the start of this explorative study. Subjects will not be replaced after withdrawal.

7.6 Follow-up of subjects withdrawn from treatment

No formal follow-up visits are planned in case a subject withdraws from the study after administration of a study investigational product.

7.7 Premature termination of the study

The study will be discontinued if the treatments are intolerable for the majority of the subjects.

8. SAFETY REPORTING

8.1 Temporary halt for reasons of subject safety

In accordance to section 10, subsection 4, of the WMO, the sponsor will suspend the study if there is sufficient ground that continuation of the study will jeopardise subject health or safety. The sponsor will notify the accredited METC without undue delay of a temporary halt including the reason for such an action. The study will be suspended pending a further positive decision by the accredited METC. The investigator will take care that all subjects are kept informed.

8.2 AEs, SAEs and SUSARs

8.2.1 Adverse events (AEs)

AEs are defined as any undesirable experience occurring to a subject during the study, whether or not considered related to the investigational product, trial procedure, or the experimental intervention. All AEs reported spontaneously by the subject or observed by the investigator or his staff will be recorded.

8.2.2 Serious adverse events (SAEs)

A SAE is any untoward medical occurrence or effect that:

- results in death;
- is life threatening (at the time of the event);
- requires hospitalisation or prolongation of existing inpatients' hospitalisation;
- results in persistent or significant disability or incapacity;
- is a congenital anomaly or birth defect; or
- any other important medical event that did not result in any of the outcomes listed above due to medical or surgical intervention but could have been based upon appropriate judgement by the investigator.

An elective hospital admission will not be considered as a SAE.

The investigator will report all SAEs without undue delay after obtaining knowledge of the events, through the web portal *ToetsingOnline* to the accredited METC that approved the protocol, within seven days of first knowledge for SAEs that result in death or are life threatening followed by a period of maximum of eight days to complete the initial preliminary report. All other SAEs will be reported within a period of maximum 15 days after the sponsor has first knowledge of the SAE.

8.2.3 Suspected unexpected serious adverse reactions (SUSARs)

Not applicable.

8.3 Annual safety report

Not applicable.

8.4 Follow-up of AEs

All AEs will be followed until they have abated, or until a stable situation has been reached. Depending on the event, follow up may require additional tests or medical procedures as indicated, and/or referral to the general physician or a medical specialist.

SAEs need to be reported until end of study within the Netherlands, as defined in the protocol.

8.5 Data Safety Monitoring Board (DSMB) / Safety Committee

Not applicable.

9. STATISTICAL ANALYSIS

The SPSS statistical software package Version 23.0.0.2 (IBM[®] SPSS Statistics, Chicago, IL, USA) will be used for statistical analysis. The data will be organized in this software, containing descriptive independent variables (ID, age, gender, BMI), fixed variables (test day (1, 2), treatment (A, B), time) and dependent variables (food intake and VAS scores). A descriptive analysis of the study population will be performed first, about the independent variables age, gender and BMI, including mean \pm S.D. The dependent variables will be checked to meet the requirements of the statistical models described, including and normality, and homogeneity of variance. Continuous data will be reported as mean \pm S.D and/or S.E.M. and statistical significance will be set at $p < 0.05$, two sided.

9.1 Primary study parameter(s)

The main study parameter is the intake of *ad libitum* meal (kcal). The difference in intake of *ad libitum* meal (kcal) will be compared within-subjects, between ingestion of the active or control yoghurt.

H_0 : There is no significant difference in *ad libitum* meal intake after control and active yoghurt.

H_1 : *Ad libitum* meal intake differs between control and active yoghurt.

If the food intake data (2 values per subject) is normally distributed and homogeneity of variance holds, a paired-samples T-test will be performed to evaluate the null hypothesis that there is no difference in *ad libitum* food intake after control and active yoghurt (n=35, $p \leq 0.05$).

Missing values of the primary study parameter food intake will be left out of the analysis, because the paired-samples T-test compares food intake within-subjects.

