4.4 Sample size calculation

The calculations on required sample size should be based on the primary outcome: difference in intake of *ad libitum* meal. To our best knowledge, however, no data is available for this particular encapsulation system, so we need to base our calculation on related studies. First, food intake was significantly reduced with 79 kcal (SEM 41; n=15 so SD of 159 kcal) after ileal intubation (of 6 g lipid; food intake 435 kcal) compared to oral ingestion (of 6 g lipid, combined with saline infusion; food intake 514 kcal) [2]. Second, food intake reduced after active micro-encapsulate intake (655 kcal, SD 216) compared to placebo (699 kcal, SD 238), so a reduction of 44 kcal (P=0.011) [*not yet published randomized placebo-controlled double-blind cross-over study in 60 healthy overweight volunteers*]. Third, intra-ileal infusion of 6 g safflower oil, the food intake (464.3 ± 90.7 kcal) was 122 kcal (21 %) lower compared to placebo (saline infusion, 586.7 ± 70.2 kcal) [1]. On average, these three studies showed a difference of 82 kcal with an average SD of 156 kcal, and we used these values to base our calculation on. For the statistical test (p-value of 5% ($\alpha = 0.05$), power 80% ($B = 0.80$)) we used the formula:

$$n = \frac{(t_{n-1,\alpha} + t_{n-1,\beta})^2}{d^2}$$

that can be estimated by:

$$n \geq \frac{\sigma^2}{\delta^2} (Z_\alpha + Z_\beta)^2$$

with σ being the standard deviation for paired samples (156 kcal), δ being the minimal detectable difference in food intake (82 kcal), $Z\alpha$ being 1.96 (for $\alpha = 0.05$), $Z\beta$ being 0.84 (for $B = 0.80$).

Filling the formula results in a value of $n \geq 28.3$, so at least 29 subjects. However, it must be noted that the sample size estimation uses Z-values, derived from a normal distribution. The statistical test, used in this sample size, is based on a t-distribution instead of the normal distribution. Thus, for small samples ($n < 100$), the sample size n must be estimated iteratively using the appropriate t-values. These t-values depend on 'degrees of freedom' (df), which corresponds to $n-1$, so in our case for a sample size n of 29, the degree of freedom is 28 (29-1). Therefore, the following formula was used:

$$n \geq \frac{\sigma^2}{\delta^2} (t_{n-\frac{1,\alpha}{2}} + t_{n-1,\beta})^2$$

with t-value being 2.048 for a two-sided α of 0.05 with df of 17, and 0.855 for β = 0.80 with df of 17.

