7.2 Randomisation, blinding and treatment allocation

All 35 participants receive two treatments of one day each, following a cross-over design. The order in which they receive the treatments will be determined through randomisation. Randomisation will minimize the risk of bias and enhance the validity of statistical comparisons. As subjects qualify for the study, they will be assigned a subject number (01 - 35, *via* lottery) that corresponds with a predefined randomization schedule.

Blinding of packing and treatment will be assured for subjects. We will check at the end of the last test day whether the subjects were expecting to consume a control on one or more of the test days, and in case yes, on which day(s) they received it. Besides, on this day we will ask how they liked the yoghurts.

The VAS questionnaires will be labelled by the researcher with study title (Lipid encapsulates, LE), subject number (01-35), yoghurt (A, B) and time point (t= 0, 30, 60, 90, 105, 120, 135, 150, 165, 180, 195, 210 min). For example: LE07/ A / 120 - Subject 07, active yoghurt, VAS scores at 120 minutes.

Besides, labelling of the products will be according to the following code: study title (Lipid encapsulates, LE), subject number (01-35), yoghurt (A, B), and date. For example: LE07/A 13-02-17 means subject 7 of lipid encapsulates study-yoghurt A (active) produced on February 13th 2017.

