9.2 Secondary study parameter- VAS scores for satiety and GI symptoms

Secondary parameters include differences between treatments in feelings of satiety (as measured by VAS) and GI symptoms (as measured by VAS). During each of the test days, participants (n=35) fill in nine VAS scores (VAS1-VAS9) per time point, at 12 time points ($t= 0, 30, 60, 90, 105, 120, 135, 150, 165, 180, 195, 210$ min). If the VAS data is normally distributed and homogeneity of variance holds, we will use a repeated measures analysis of variance (ANOVA) model that includes the fixed factors treatment, time, and the interaction treatment * time to evaluate the null hypothesis that there is no difference in VAS scores after control and active yoghurt (n=35, $p \leq 0.05$). If the results of the ANOVA indicate a significant effect of intervention yoghurt (Wilks' Lambda test, $p \leq 0.05$), the treatments will be compared based on pairwise comparison with a Tukey post hoc test.

Missing values of the secondary study parameter will cause the intervention to be left out, due to the use of ANOVA.

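### Section 9.1 makes the primary paired t-test depend on normal raw intakes with equal variances, which the test does not need, and names no alternative

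*Combined protocol and SAP*

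**What the plan says.** Section 9.1 opens the primary analysis with "If the food intake data (2 values per subject) is normally distributed and homogeneity of variance holds"; only then, it says, "a paired-samples T-test will be performed to evaluate the null hypothesis that there is no difference in" intake between the two yoghurts. Two values per subject are the raw intakes, since a difference is one value per subject. The introduction to section 9 points the same way: "The dependent variables will be checked to meet the requirements of the statistical models described, including and normality, and homogeneity of variance", and it lists these as "and dependent variables (food intake and VAS scores").

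No section names an analysis to use if the condition is not met, and none names the assumption test or its cut-off. Section 9.2 puts the same open condition on the VAS scores.

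Section 4.4, by contrast, sizes the trial on the differences, with σ "being the standard deviation for paired samples (156 kcal").

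On treatment order, section 7.2 gives each subject a number "that corresponds with a predefined randomization schedule" without saying whether the schedule balances the two orders. Section 9 lists test day as a variable in the data file. It enters neither the t-test in 9.1 nor the 9.2 ANOVA, a "model that includes the fixed factors treatment, time, and the interaction" of treatment and time.

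**The concern.** A paired t-test is a one-sample t-test on the within-subject differences. Men and women aged 18 to 65 can differ widely in how much they eat, so the raw intakes can be skewed while the differences are close to normal. The stated check would then reject a test that is sound.

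The plan is silent on what follows. The one confirmatory comparison would have no prespecified method, and a signed-rank test, a log transformation or the t-test after all could be chosen once the results were visible. A log transformation would also turn the effect into a ratio, although section 7.1.1 defines the endpoint in kcal.

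Test day is a separate and lesser point. Leaving it out is not an error, but adjusting for it would protect precision if intake shifts between the first and second visit.

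**Working it through.** **1. The plan's own figure.** Section 4.4 gives σ = 156 kcal and δ = 82 kcal, so (156/82)² = 3.619.

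- Normal quantiles: 3.619 × (1.96 + 0.84)² = 28.4 (the plan prints 28.3), so 29.
- t quantiles with 28 df: 3.619 × (2.048 + 0.855)² = 30.5. Iterating to 30 df gives 30.36, so 31, as stated.
- Non-central t power: 80.8% at n=31 and 85.6% at n=35.

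Only the SD of the differences enters. The shape and spread of the raw intakes do not.

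**2. What the test requires.** Write intake as subject level + treatment effect + error. The statistic is t = d̄ / (s_d/√n), and subject level cancels in each difference d. Skew in subject levels makes the raw intakes non-normal and leaves d untouched. Unequal variances under the two yoghurts change the variance of d, which s_d estimates directly.

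**3. A plausible raw spread.** Section 4.4 cites one study of 60 volunteers: "active micro-encapsulate intake (655 kcal, SD 216) compared to placebo (699 kcal, SD 238), so a reduction of 44 kcal (P=0.011"). I assume that P value comes from a paired t-test with 59 df.

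- t = 2.626, so the SD of differences is 44/2.626 × √60 = 130.
- Pooled raw SD: √((216² + 238²)/2) = 227.
- Between-subject SD: √(227² − 130²/2) = 208, or 199 with 156 in place of 130.
- On the mean of 677 kcal, that is a log-SD of 0.30 (0.29 with 156).

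Log-SDs of 0.15 and 0.20 are added as milder assumptions.

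**4. How often the condition fails.** Assumptions: log-normal subject means, normal within-subject error, and failure when Shapiro-Wilk gives p<0.05 on either raw column (6,000 to 8,000 simulated trials per cell).

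| Scenario | n=31 | n=35 |
|---|---|---|
| Raw intakes exactly normal | 9-10% | 9-10% |
| Log-SD 0.15 | 12-13% | 11-14% |
| Log-SD 0.20 | 16-19% | 17-20% |
| Log-SD 0.29-0.30 | 30-36% | 33-40% |
| Check on the differences instead | about 5% | about 5% |

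A Levene test on the two columns adds at most 3 points here. Harsher assumptions go much further. With a more strongly skewed subject level the condition failed in about 74% (n=31) and 79% (n=35) of trials. With normal intakes and raw SDs of 260 and 160 it failed in about 77% and 85%. In those cases too the unconditional t-test stayed near 5% type I error, with about 80% power at n=31.

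**5. What a failure can do.**

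- Unconditional paired t-test under log-SD 0.29-0.30: type I error 5.0-5.2%.
- Free choice of paired t, signed-rank or log-scale t after a failed check (n=35, intakes floored at 20 kcal for the log): 6.1-6.9% in those trials, 5.2-5.7% overall.
- At a true 82 kcal the three tests disagree on significance in 5-12% of trials.
- Power at n=35, SD 156, log-SD 0.29: t 86%, signed-rank 84%, log-scale t 82%.

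**6. Test day.** The documents give no period effect, so shifts of 50 and 80 kcal are assumed: each difference gains +shift or −shift according to order. The adjusted analysis has SE = (156/2) × √(1/n₁ + 1/n₂) on n−2 df.

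| Split of orders | Adjusted SE (kcal) | Adjusted power | Paired-test type I error, shift 50 / 80 |
|---|---|---|---|
| 16:15 | 28.0 | 80.7% | 4.0% / 2.9% |
| 18:13 | 28.4 | 79.7% | 4.8% / 4.5% |
| 20:11 | 29.3 | 77.2% | 6.5% / 8.5% |

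Under unrestricted allocation at n=31, a split of 18:13 or worse has probability 0.47 and 20:11 or worse 0.15; averaged over such splits the paired test's type I error is about 5%. At 18:13 a 50 kcal shift moves the unadjusted estimate by 50 × 5/31 = 8 kcal, 0.3 of its standard error (156/√31 = 28 kcal).

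At 16:16 (n=32), if 156 excludes period variation, paired-test power falls from 82% to 79% and 75% for the two shifts, while the adjusted test stays at 82%. If 156 already contains it, the SDs net of period are √(156² − 50²) = 147.8 and √(156² − 80²) = 133.9. Power is then 83% and 86% paired, and 86% and 92% adjusted. Adjustment gains about 3 and 6-7 points either way.

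**The case against.** The plan plainly intends a paired t-test: the trial is sized on paired differences, 9.1 compares intake within subjects, and its missing-data rule is justified by the pairing. The introduction to section 9 speaks of checking the requirements of the models described, which for a paired test could be read as the differences. The trial calls itself explorative, and the type I error figures are small; the 5.2% cell, from 20,000 runs, cannot be told from 5.0%. The failure rates rest on an assumed check and an assumed shape, and the period shifts are invented.

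Much of this is fair, and it limits the weight of the point. The failure rates are illustrations, and test-day adjustment is a preference with a cost when the orders are unequal. The core survives. The parenthesis in 9.1 specifies raw values, the list in section 9 supports it, and equal variance has no role in a paired test on any reading. Even on the generous reading no fallback is named. The explorative label does not help, because the plan states a primary hypothesis, a two-sided 5% level and 80% power.

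**Conclusion.** The concern holds. The rule that decides the primary test looks at the wrong quantity, and the plan has no primary analysis when that rule fails. This should be corrected, but it does not undermine the design: the paired t-test is suitable and 31 completers is right.

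The firm part needs no simulation: it follows from the wording and from what a paired t-test is. The size is moderate and conditional. It depends on a formal test at 5% on each column, on the log-normal spread, and on how freely a replacement would be chosen. Under those assumptions the main cost is an open choice in a non-trivial share of trials, with only a small rise in type I error. The test-day figures rest wholly on assumed shifts and splits, and support a recommendation only.

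**What to change.** In 9.1, delete the condition on raw normality and homogeneity of variance and fix the test. Suggested text:

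> Intake (kcal) will be analysed with a linear model with subject, treatment and test day (1, 2). The active-control difference is reported with its 95% CI and two-sided p-value. Normality is checked on the within-subject differences, centred within treatment order; the result does not change the primary test. Sensitivity analysis: rank-sum test between the two orders on the day 1 minus day 2 differences, with half the Hodges-Lehmann shift (active-first minus control-first), and half its confidence limits, as the treatment-effect estimate.

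The check belongs on order-centred differences. With exponential differences at n=31, Shapiro-Wilk detects the departure in 92% of trials there, but in 46% on the residuals of the two-value model.

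Minimum version, if test day is left out: keep the paired t-test unconditionally, check the differences, and name the signed-rank test as sensitivity analysis. This costs nothing.

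Both versions are changes of wording, with 31 completers and 35 recruited unchanged. The adjusted model spends one degree of freedom. Without a period effect its power at n=31 is 80.7% at 16:15, but 79.7% at 18:13 and 77.2% at 20:11, against 80.8% unadjusted, so the plan should also say whether the schedule balances the orders. The rank-sum sensitivity test has about 77% power at 16:15. The t-based result stays primary even if the differences look skewed, with the rank-based result beside it.

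In 9.2, state what follows if the condition on the VAS data fails, or remove it. Test day cannot simply be added to that repeated-measures ANOVA. If adjustment is wanted, use a mixed model (subject and subject-by-test-day random; treatment, time, their interaction and test day fixed), or enter treatment order as a between-subject factor. That is a change of model and is optional.

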This leads, after a small number of iterations, to a re-estimate of n of at least 31 subjects ($n \geq 30.4$). According to this power calculation, 31 subjects will need to complete the study. Because of possible dropouts, 35 subjects will be recruited for this study.

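### The primary paired t-test has no test-day term and no order balance is stated, so any day 1 to day 2 shift in intake is counted as error and, with unequal orders, biases the estimate

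*Combined protocol and SAP*

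**What the plan says.** Section 9.1 compares lunch intake within subjects. Subject to normality and homogeneity of variance, "a paired-samples T-test will be performed to evaluate the null hypothesis" of no difference between the two yoghurts. Subjects missing an intake value drop out of this comparison.

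Section 9 lists "fixed variables (test day (1, 2), treatment (A, B), time") for the dataset, so the period variable will be available. Neither stated analysis uses it. The VAS analysis in section 9.2 is a repeated measures "model that includes the fixed factors treatment, time, and the interaction" of those two factors, again without test day.

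Section 7.2 says that treatment order is randomised: each subject draws a number "that corresponds with a predefined randomization schedule". It gives no ratio, blocking or count per order.

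Section 4.4 plans on 82 kcal, with σ "being the standard deviation for paired samples (156 kcal"), and concludes: "According to this power calculation, 31 subjects will need to complete the study". Thirty-five are recruited, and section 7.5 adds: "Subjects will not be replaced after withdrawal".

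**The concern.** Every subject eats the same test lunch twice, at least a week apart. Intake may differ between the first and second occasion for reasons unrelated to the yoghurt, such as familiarity with the meal or the setting. In a two-period cross-over, such a shift pushes the active-minus-control difference one way in subjects who take the active yoghurt first and the other way in those who take it second.

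A paired t-test pools the two groups as if they had one common mean. Two things follow:

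- The separation between the order groups enters the SD of the differences. The standard error grows and the confidence interval is wider than it needs to be.
- If the orders are unequal, the shift does not cancel from the mean, and the estimate is biased in the trial actually run.

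Thirty-five is odd, the schedule's balance is not stated, withdrawals are not replaced and incomplete pairs are dropped. Exact balance in the analysed set is therefore not assured.

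**Working it through.** **Inputs from the documents.** Effect 82 kcal, SD of paired differences 156 kcal, two-sided α 0.05, power 80%, 31 completers, 35 recruited (section 4.4).

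**Assumed.** P is day 2 minus day 1 intake. The documents give no figure, so 25, 50 and 80 kcal are used as a range.

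**The plan's own figure.**
- With z-values: (156/82)² × (1.96 + 0.84)² = 3.619 × 7.84 = 28.4, so 29.
- With the t-values printed in 4.4: 3.619 × (2.048 + 0.855)² = 30.5. Iterating on n − 1 df gives 30.4, so 31.
- Exact noncentral-t power at n = 31 is 80.8%. The stated sample size is reproduced.

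**Model.** Let d be active minus control and τ the treatment effect. Then d has mean τ − P in order AB and τ + P in order BA, with SD 156 within each order.
- Paired mean: τ + P(n_BA − n_AB)/N.
- SD seen by the paired test: about √(156² + 4P²·n_AB·n_BA/N²).
- Test-day-adjusted estimate: the average of the two order means, with SE = (156/2)·√(1/n_AB + 1/n_BA) on N − 2 df. It does not depend on P.

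**Near balance, n = 31, orders 16/15 (simulated).** The ranges cover which order has the extra subject.

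| P (kcal) | Power, paired t | Power, adjusted | Bias (kcal) | Type I error, paired |
|---|---|---|---|---|
| 25 | 79.3–80.7% | about 80.7% | 0.8 | about 4.8% |
| 50 | 76.2–79.5% | about 80.7% | 50 × 1/31 = 1.6 | about 4.0% |
| 80 | 70.2–75.9% | about 80.7% | 80 × 1/31 = 2.6 | about 2.8% |

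**Confidence interval at 16/15.**
- Paired, P = 50: the expected sample SD of the differences is 164.1, so the 95% half-width is 2.042 × 164.1/√31 = 60.2 kcal.
- Paired, P = 80: the SD is 175.9 and the half-width is 64.5 kcal.
- Adjusted: 2.045 × 78 × √(1/16 + 1/15) = 57.3 kcal in either case.

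**An 18/17 schedule with four random losses.** The result is 16/15, one way or the other, in 39.7% + 26.5% = 66% of cases. Averaged over the direction of the shift, paired power is about 80%, 78% and 73% at P = 25, 50 and 80, against about 80.5% adjusted. Mean absolute bias at P = 50 is 2.8 kcal.

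**Unrestricted order (an assumption about the schedule).**
- At n = 31, paired power is 79.8%, 76.9% and about 71% at P = 25, 50 and 80, against about 79.3% adjusted.
- With N = 35, a split of 22/13 or worse has probability 2 × P(Bin(35, 0.5) ≥ 22) = 17.5%. At 22/13 and P = 50 the bias is 50 × 9/35 = 12.9 kcal and type I error is about 6.3%.
- Averaged over all unrestricted allocations, the estimate is unbiased and type I error is 5.0%.

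**Price of adjusting when P = 0 (exact).**

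| Split | Paired t | Adjusted |
|---|---|---|
| 16/15 | 80.84% | 80.71% |
| 18/17 | 85.56% | 85.47% |
| 18/13 | 80.84% | 79.72% |
| 22/13 | 85.56% | 83.06% |
| 20/11 | 80.84% | 77.24% |

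**The case against.** Several fair points can be made for the plan as written.

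- **No shift is shown.** The fast, clock times and breakfast are the same on both days, and P = 80 is nearly the whole planned effect. If P is zero, the paired t-test is valid and marginally more powerful. At P = 25 the gain is small or nil, and under unrestricted order the paired test is slightly ahead (79.8% against 79.4%). This stands, and it is why the size is conditional.
- **The SD of 156 may already include period variance.** For one of the three source studies, section 4.4 back-calculates the SD from a standard error of the difference. If the total SD is held at 156, paired power at 16/15 and P = 50 is about 80–83%, so planned power is not lost. Adjustment then raises it to about 85%. The documents do not settle which case applies.
- **All 35 may complete.** At 18/17 and P = 50, paired power is about 82–84%, still above target, against 85.5% adjusted.
- **The schedule may be balanced.** If so, bias is negligible and the paired test errs on the conservative side. The 22/13 figures describe one possible outcome of an unrestricted list and should not carry much weight.
- **The trial is exploratory, and the paired test matches the sample-size method.** That makes it a defensible choice. It does not make it the better one when the period variable is recorded and adjusting for it costs almost nothing near balance.

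**Conclusion.** The concern holds as an inexpensive improvement to the primary analysis. It is not a flaw that invalidates the trial. No stated model uses test day, and no order balance is specified.

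Near balance, the consequence of a shift is lost precision: roughly 1 to 4 points of power at an assumed P of 50 kcal and 5 to 11 at 80 kcal, with bias of 1 to 3 kcal and a conservative test. Bias large enough to matter against 82 kcal needs both a substantial shift and clearly unequal orders, which is plausible only if the schedule is unrestricted.

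These power losses assume that P adds to the planning SD of 156 kcal. If 156 already includes it, the stated power is kept and adjustment is a gain on top. Nothing here shows that the power calculation fails. Confidence is medium, because P and the content of the schedule are unknown.

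**What to change.** **Section 9.1**, replacing the paired t-test as primary:

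> The primary analysis is a linear mixed model of ad libitum intake (kcal) in subjects with both test meals, with treatment (A, B) and test day (1, 2) as fixed effects and subject as random effect. The A − B contrast with its two-sided 95% confidence interval is the primary result. The paired-samples t-test is a sensitivity analysis.

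The normality and variance checks now in 9.1 should then be applied to the model residuals.

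**Section 7.2**, added:

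> The predefined schedule allocates 18 subjects to one order and 17 to the other.

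If the schedule already exists, the sentence should report its actual split. Both changes should be made before any intake data are examined.

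**Cost.** Two sentences and one degree of freedom. With no period shift, the power given up is 0.1 points at 16/15 or 18/17 and 1.1 points at 18/13. It averages about 1.5 points under unrestricted order and reaches 2.5 at 22/13 and 3.6 at 20/11. Stating 18/17 keeps it near the low end. The required number of completers stays at 31.
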